After a series of qualitative and quantitative studies to understand how home, faith and work settings influenced healthy eating, physical activity and tobacco use conducted from 2004 to 2010,^{32,44-50} the EPRC Community Advisory Board (CAB) prioritized obesity prevention through home environments as the focus of our intervention research. Using Community Based Participatory Research (CBPR) in collaboration with our CAB in SW GA, we developed and tested the HH/HF intervention, which was originally delivered through home visits and telephone calls. The intervention involves a tailored home environment profile and a health coach working with participants to select and implement a series of healthy actions to create a home environment more supportive of healthy eating and physical activity (see Table 1). Healthy actions were selected based on an extensive review of the literature to identify features of the home associated with dietary behavior and/or weight-related outcomes.

Table 1. Sample of Healthy Actions for HH/HF intervention

Healthy Eating Actions

Always have a low calorie beverage available instead of sugar soda and/or sweet tea.
Identify one unhealthy food or drink and do not allow it in the home.
Bring home fresh vegetables and fruits at least once a week and make them easy to see and grab.
Establish rules that limit eating while watching TV.

Healthy Physical Activity Actions

Keep at least one piece of exercise equipment or aid in a visible location and commit to using it once a week.
Identify and commit to walking to a place in your neighborhood at least once a week.
Establish a rule for screen free hours/days and use the time for exercise.

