Data Analysis Plan for the assessment of implementation study (aim 2)

Descriptive analyses will be run on survey and coaching log/web analytic data to characterize the process measures and program implementation. Regarding data from 2-1-1 and Horizons leaders and staff, we will conduct analyses pooled across sites and by individual sites (i.e., the four 2-1-1s and Horizons versus EPRC) to understand variations in promotion, recruitment, and implementation. We will also develop a codebook based on evaluation questions and emergent themes from the transcripts. Two analysts will double code each transcript and resolve discrepancies through discussion. NVivo will be used for qualitative data analysis and management. We will then generate code reports using NVivo to facilitate identification of themes and develop matrices to aid in identifying themes and patterns across key categories such as type of 2-1-1 organization (e.g., Atlanta versus Macon/Columbus versus Albany), which differ in terms of staffing structure and organizational and community context. A similar approach will be taken for the analysis of qualitative data from intervention arm participants. The process evaluation data from program participants will be triangulated with the staff interviews to assess multiple stakeholders' perspectives.

Data Analysis Plan for the cost-effectiveness analysis (aim 3)

We will conduct a cost analysis and a cost-effectiveness analysis of the intervention, focusing on effects associated with improvements in diet (i.e., fruit and vegetable consumption, fewer empty calories) and avoidance of weight gain (relative to controls). The analysis will be conducted from the societal perspective and assume a lifetime horizon. We will use estimates of effectiveness of the intervention based on the analysis described above. In the baseline analysis, we will assume that behaviors persist for participants remaining lifetime. We will test the sensitivity of results to reasonable assumptions about effect durability, but most studies linking dietary behaviors to health outcomes in the literature focus on binary classifications of behaviors rather than exposure time. We will build a model that tracks participants from the beginning of the intervention to death. The analysis will conform to Panel on Cost-Effectiveness in Health and Medicine standards for conducting cost-effectiveness analyses.⁶⁸

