Direct intervention costs. We will estimate the costs of program delivery in the intervention group. We will not consider costs associated with the evaluation of the intervention. Project staff will be asked to keep time logs to document time spent on developing and delivering the intervention. We will value staff time based on their wages, which are included in the grant budget. For staff who are hired on a full-time basis, we will make a reasonable assumption about the share of time they spend on intervention delivery versus research and value it accordingly. **Indirect costs.** We will record the length of time participants spend on the phone with their Coach and value time using the median US wage. Use of a wage to value time costs is appropriate even for individuals who are not employed because it reflects the opportunity cost of forgone leisure time. **Cost-offsets.** We will focus on the impact of the intervention on fruit and vegetable consumption and obesity. We will follow the methods of Rahkovsky and Gregory to estimate cost-offsets from changes in fruit and vegetable consumption.⁶⁹ They estimate the relationships between food prices and non-high density lipid cholesterol and use their results to predict the impact of interventions to change the consumption of various types of food groups (e.g., vegetables, whole grain products) on cardiovascular disease-related spending. We will use estimates from the nutritional epidemiology literature and estimates of disease-attributable costs, some of which we have estimated,⁷⁰ to predict the impact of dietary changes on cancer- and diabetes-specific costs. We will use a similar approach to estimating cost-offsets from reductions in obesity that occur independently of dietary improvements.

Cost-effectiveness. In the event cost-offsets are lower than the direct costs of the intervention (i.e., it is not cost-saving), we will calculate the incremental cost-effectiveness ratio associated with improvements in health status due to the intervention. The numerator of the ratio is the change in per participant costs between the two groups, including the direct costs of the intervention, indirect costs, and cost offsets. The denominator is the change in quality-adjusted life years.

TRAINING OF THE STUDY TEAM

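### Aim 3 is labelled societal, yet it names no household food cost or food-related time while crediting the health benefit of changed purchasing and cooking for life

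*Combined protocol and SAP*

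**What the plan says.** The section Data Analysis Plan for the cost-effectiveness analysis (aim 3) sets the frame: "The analysis will be conducted from the societal perspective and assume a lifetime horizon". On durability it says: "In the baseline analysis, we will assume that behaviors persist for participants remaining lifetime", with a sensitivity analysis on how long the effect lasts. It adds a commitment to a published standard: "The analysis will conform to Panel on Cost-Effectiveness in Health and Medicine standards for conducting cost-effectiveness analyses".

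The same section then names three kinds of cost:

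- Direct: "We will estimate the costs of program delivery in the intervention group".
- Indirect: "We will record the length of time participants spend on the phone with their Coach and value time using the median US wage".
- Cost-offsets, meaning disease-related spending: "We will focus on the impact of the intervention on fruit and vegetable consumption and obesity".

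The numerator of the ratio is the between-group change in cost per participant, "including the direct costs of the intervention, indirect costs, and cost offsets". The ratio is calculated only if the offsets fall short of the direct costs; otherwise the programme counts as cost-saving.

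Field Methods for cost-effectiveness study (aim 3) gives the data sources: delivery tracking logs, partners' time and cost estimates, call-attempt data and process questions in the participant survey.

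On the intervention side, Table 1 includes the action "Bring home fresh vegetables and fruits at least once a week and make them easy to see and grab". The Intervention Condition section tailors the home profile on, among other things, produce shopping, fast-food and restaurant purchases for family meals, and food preparation.

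**The concern.** The programme is meant to work by changing what a household buys and how it prepares food. Any resulting change in the food bill, or in time spent shopping and cooking, falls on the participant's household. An analysis presented as societal would be expected to count it or say that it is left out. The plan does neither.

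The lifetime base case makes this matter more. Coaching is paid for once, over 12 weeks. The health gain and the medical savings then run until death because the behaviour is assumed to continue. The household cost or saving of continuing it is a recurring item too, but it enters at zero every year.

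At stake is how the Aim 3 result is read. A ratio or a cost-saving statement labelled societal would rest on an unstated assumption that households' food costs and food-related time do not change. Users could care about that: in the 2-1-1 feasibility study all participants reported household incomes below $25,000.

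**Working it through.** **Step 1. Label against contents.** The documents state no Aim 3 cost, wage, discount rate, QALY gain or ratio, so there is no figure to reproduce. The main check is a comparison of the text.

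| Item | Named as a cost? | Aim 3 data source named? |
|---|---|---|
| Programme delivery, including staff and partner time | Yes, direct | Yes |
| Participant time on coaching calls | Yes, indirect | Yes |
| Disease-related spending | Yes, offset | Modelled from literature |
| Household food spending | No | No |
| Shopping and cooking time | No | No |

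Food prices do appear, but only inside the cited method for predicting cardiovascular spending. They are not used to cost the household's purchases.

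**Step 2. Does the intervention act on the missing items?** Table 1 and the profile tailoring target food shopping, preparation and meals from outside the home. Table 2 (the earlier randomised trial) and the feasibility study report changes in these behaviours. They report no change in dollars or minutes, so a change in resource use is an inference.

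**Step 3. Illustration: food spending.** All inputs are assumptions. The change is $1 per week, so 52 × $1 = $52 a year. The discount rate is 3%. The horizon is 30 years, or 40 as a longer case, chosen because mean age in the feasibility study was 44. Mortality is ignored. With payments at the start of each year:

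A(T) = 1.03 × (1 − 1.03^−T) / 0.03

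- A(30) = 1.03 × 19.60 = 20.19, so $52 × 20.19 ≈ $1,050.
- A(40) = 1.03 × 23.11 = 23.81, so $52 × 23.81 ≈ $1,238.
- 30 years undiscounted: $52 × 30 = $1,560.
- If the behaviour lasts one year only: $52.

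The amount is proportional to the weekly change: $2 gives about $2,100 and $5 about $5,250 (30 years, 3%). A saving has the same size with the opposite sign.

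**Step 4. Illustration: time.** Table 3 schedules six calls. At an assumed 15 to 45 minutes and $15 to $25 an hour, the counted time is 6 × 0.25 × $15 = $22.50 to 6 × 0.75 × $25 = $112.50, once. An assumed 10 extra minutes a week is 10 × 52 / 60 = 8.67 hours a year. At $15 an hour that is $130 a year, and $130 × 20.19 ≈ $2,620. At $25 it is about $217 a year, or roughly $4,370.

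**Step 5. Effect on the ratio.** The shift is the household amount divided by the QALY gain. For $1,050 and assumed gains of 0.02, 0.05 and 0.10 QALY, it is $52,500, $21,000 and $10,500 per QALY.

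**Step 6. The cost-saving rule.** Write D for direct costs, I for indirect costs and O for offsets. The plan computes a ratio only when O < D. If D ≤ O < D + I, it would call the programme cost-saving although the costs it names itself exceed the offsets. That gap is I wide, about $23 to $113 on the inputs of Step 4. Adding household costs to the numerator alone would not change this test.

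**Step 7. The threshold that is needed.** With w the weekly household change in dollars (food cost plus valued time), A(T) at the duration used for the benefit, ΔQ the QALY gain and λ a chosen value per QALY:

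- Cost saving is lost when w > (O − D − I) / (52 × A(T)).
- The ratio crosses λ at w = (λ × ΔQ − D − I + O) / (52 × A(T)).

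Every other term is already an output of the planned model.

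**The case against.** Several points on the other side have weight.

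- **The list may not be closed.** The numerator sentence says what it includes, and the plan commits to Panel standards whose content is not in these documents. So one cannot say that food costs are ruled out. But no further component is named and no Aim 3 data source is given for one. The point stands as an item not named, and it does not rely on the Panel's requirements.
- **The plan is partly societal already.** It values participants' call time at a wage, including for people without paid work, because leisure given up has a cost. That is a fair defence against calling it a payer analysis. The same reasoning would apply to shopping and cooking time.
- **The household effect may be small or a saving.** The Intervention Condition section describes the actions as low in cost. Each participant chooses three of eight, so not everyone takes up weekly produce. Other actions replace or remove items, take-out meals may fall, and earlier studies report lower energy intake. All of this stands and leaves the sign open. It argues for a threshold analysis; it does not support an unstated zero.
- **Durability is tested.** Lifetime persistence is only the base case, and a shorter effect would shrink the omitted item as well. However, that sensitivity analysis varies how long the benefit lasts, and the household item remains zero at every duration.

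A reader might go further and infer that the omitted item exceeds the whole programme cost, or that it would reverse a cost-saving or cost-effectiveness conclusion. The documents do not support that. They give no programme cost, QALY gain or spending change to compare it with, so either outcome is only a possibility. Nor do they support saying that the programme raises households' food bills.

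**Conclusion.** The concern holds as a mismatch between label and contents, made more important by lifetime persistence. The base case carries the health benefit of changed purchasing and cooking for life and, as written, sets the recurring household cost or saving to zero.

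The direction and size of the resulting error cannot be determined from the documents. The figure of about $1,050 per participant for each $1 a week rests on assumed inputs: 30 years, 3%, payment at the start of each year and no mortality. It shows how strongly a small weekly amount accumulates under the plan's own persistence assumption; it is not an estimate of the bias.

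A related inconsistency is that cost saving is judged against direct costs alone, which leaves out even the participant time that the plan counts elsewhere. The point is confined to Aim 3. The HEI analysis under Aim 1 and the implementation work under Aim 2 are unaffected.

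**What to change.** In the Aim 3 data analysis plan:

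1. Describe the perspective by what is counted: programme costs, participant call time and health-care costs. Alternatively, call it a partial societal perspective and list household food spending and shopping or cooking time as exclusions.
2. Add a threshold analysis giving the weekly change in household food cost, and in shopping or cooking time, at which the conclusion changes. Run it in both directions and under the same durability assumptions as the benefit, so that a shorter effect shortens both.
3. Apply the cost-saving test to all included costs: direct plus indirect, and the household items as well in the threshold scenario.

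The cost is a few sentences of plan text, one extra model scenario and a less ambitious label. No new data are needed. Adding a survey question on weekly food spending would not by itself justify the full societal label, because food-related time would still be uncounted. As the protocol is at Version 7, dated 1/24/24, some participants may also be past follow-up already.

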key aspects of motivational interviewing, such as reflective listening and rolling with resistance.^{64,65} Immediately after a participant completes baseline data collection, we will generate the home environment profile via a secure web-based application and send it along with the other intervention materials (i.e., family contract, healthy action checklist and stickers). The home environment profile presents tailored baseline data in a user-friendly format that helps participants identify aspects of their home environment that facilitate or hinder eating healthy. Tailoring is based on the household food inventory, frequency of grocery shopping for fruits and vegetables, frequency of purchasing fast food/restaurant food for family meals, food preparation and serving practices, eating in front of the TV, and weight monitoring.

The intervention will be delivered over 12 weeks with weekly contact alternating between phone and text/e-mail contact (see Table 3). The Coach will contact the participant one week after baseline data collection to review

the home environment profile and select the first healthy action. On the first call, the Coach will review the profile, then present a list of low-cost “healthy actions” that target possible environmental changes to make in the home. Using a series of open-ended questions, the coach guides the participant to select a healthy action to work on. This will be followed at weekly intervals by text/e-mail check-ins to reinforce progress and problem-solve challenges. Additional healthy actions are added in future calls, for a total of three healthy actions across three months. The participant will document the selected healthy actions on a family contract with stickers and their signature. The coaching calls, text messages and intervention materials are designed to increase behavioral capability, self-efficacy and behavioral intention to improve the home food environment for healthy eating and weight gain prevention. Participants will receive three seasonings, one portion size plate, and a magnetic grocery list pad after completing their 3rd coaching call.

Control Condition. Participants in the control condition will receive two mailings on healthy eating, the first from the *Dietary Guidelines For Americans*

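### The cost-saving test that triggers the cost-effectiveness ratio counts direct costs only, while the ratio's own societal numerator also counts participant time

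*Combined protocol and SAP*

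**What the plan says.** All of this is in the combined protocol and SAP, mainly under Data Analysis Plan for the cost-effectiveness analysis (aim 3).

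- **Scope and perspective.** "We will conduct a cost analysis and a cost-effectiveness analysis of the intervention", and "The analysis will be conducted from the societal perspective and assume a lifetime horizon".
- **Direct intervention costs.** "We will estimate the costs of program delivery in the intervention group". Staff time is valued at wages.
- **Indirect costs.** "We will record the length of time participants spend on the phone with their Coach and value time using the median US wage". The plan applies this to people without a job as well.
- **Trigger for the ratio (Cost-effectiveness paragraph).** The ratio is calculated "In the event cost-offsets are lower than the direct costs of the intervention (i.e., it is not cost-saving").
- **Numerator (next sentence).** The plan takes the between-group difference in cost per person and describes it as "including the direct costs of the intervention, indirect costs, and cost offsets".
- **Control arm (Control Condition).** "Participants in the control condition will receive two mailings on healthy eating". The plan does not say whether the cost of these mailings is subtracted in the numerator.

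**The concern.** The plan treats direct costs, participant time and offsets as three separate items. Its test for cost-saving uses two of them, and its numerator uses all three. Two adjoining sentences therefore give different answers to the question of whether the programme saves money.

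Cost-saving is the most favourable conclusion that Aim 3 can reach. An analyst who follows the rule as written could attach that label, and report no ratio, when the plan's own numerator shows a positive net cost to society.

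**Working it through.** The plan gives no figure for any cost, offset or ratio, so there is nothing to reproduce. The check compares the two rules algebraically and then sizes the gap under stated assumptions.

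**Definitions, per participant.** D = direct cost, I = participant time cost, O = offsets, C = control-arm delivery cost (0 if not netted).

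- Rule as written: cost-saving if O ≥ D.
- Numerator: N = D + I − O − C, which is zero or less when O ≥ D + I − C.

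**Case C = 0.** The rules disagree when D ≤ O < D + I, a band of width I. Illustration with assumed D = $200 and I = $60:

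| O | Rule as written | N = 200 + 60 − O |
|---|---|---|
| $150 | not cost-saving, ratio | +$110 |
| $200 | cost-saving | +$60 |
| $230 | cost-saving | +$30 |
| $259 | cost-saving | +$1 |
| $260 | cost-saving | $0 |
| $300 | cost-saving | −$40 |

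The label is wrong from $200 up to, but not including, $260.

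**Case C > 0.**

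- If C < I, the band is D ≤ O < D + I − C, with width I − C.
- If C = I, there is no disagreement.
- If C > I, the direction reverses. For D + I − C ≤ O < D, the rule denies the cost-saving label although N is zero or negative.

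**Size of I if all six calls are completed.** Table 3 (Intervention Delivery Schedule) lists calls in weeks 1, 3, 5, 7, 9 and 11. Call length and wage amount are not given; 15 to 30 minutes and $18 to $25 per hour are assumed.

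- Low: 6 × 0.25 h × $18 = $27
- High: 6 × 0.5 h × $25 = $75

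Wider assumptions of 10 to 45 minutes and $15 to $30 per hour give 6 × (10/60) × 15 = $15 to 6 × (45/60) × 30 = $135.

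**Size of I at pilot completion.** In the 2-1-1 feasibility study, 75% completed the first call and 51% completed at least four of six. So 51% had 4 to 6 calls, 75% − 51% = 24% had 1 to 3, and the other 25% are taken as having none.

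- Mean calls, low: 0.51 × 4 + 0.24 × 1 = 2.28; cost 2.28 × 0.25 × $18 = $10.26
- Mean calls, high: 0.51 × 6 + 0.24 × 3 = 3.78; cost 3.78 × 0.5 × $25 = $47.25

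**Netting the mailings.** At an assumed $1 to $5 per mailing, two mailings give C = $2 to $10.

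- Six calls: 27 − 10 = $17 to 75 − 2 = $73
- Pilot completion: 10.26 − 10 = $0.26 to 47.25 − 2 = $45.25

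At the lowest time cost, a mailing cost above 10.26 / 2 = $5.13 each would reverse the direction.

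**The case against.** The strongest reply is that the trigger is shorthand. The plan commits without condition to a cost analysis and a cost-effectiveness analysis, sets a societal perspective, and defines the full numerator. A competent analyst would compute that numerator and see its sign.

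Part of this stands. A reader might infer that the plan forbids the ratio, or hides the net cost, when offsets reach direct costs. The text does not say so: the absence of a ratio follows only from the conditional wording, and the promised cost analysis may show the components. But the shorthand reading does not fit the words. The next sentence names direct and indirect costs as different items, the parenthesis makes the narrow comparison the meaning of not cost-saving, and no other section corrects it.

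A reader might also infer that the error always favours the programme. That holds if control-arm costs are not netted, or are smaller than the participant time cost. The plan leaves netting open, so the direction is conditional.

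The objection that the dollar ranges rest wholly on assumptions is also correct. They show the order of size and do not demonstrate a material effect.

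**Conclusion.** The trigger is wrong as written, and the point is minor. It contradicts the numerator in the same paragraph and the societal perspective set for the analysis. This textual finding is firm and needs no outside figure.

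The practical effect is confined to a band of width I, or I − C if control costs are netted and are smaller than I. Under the narrower assumptions, I is about $27 to $75 per participant for six completed calls and about $10 to $47 at pilot completion. Inside the band with C = 0, the net cost that goes unrecognised cannot exceed I.

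A reader might infer that the Aim 3 conclusion is likely to be wrong. The documents do not support that: they give neither direct costs nor offsets, so the chance of landing in the band is unknown. The primary HEI analysis is untouched.

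**What to change.** Define cost-saving as a numerator of zero or less, where the numerator is the between-group change in per-participant costs: direct plus indirect costs minus offsets. Use that same quantity as the cost test for the ratio and for any cost-saving statement, in the base case and in the effect-durability sensitivity analyses already planned.

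Report incremental costs and incremental QALYs in every case, and calculate the ratio when both are positive. The second condition avoids a ratio that is undefined or misleading when the QALY change is zero or negative. State whether control-arm mailing costs are netted; the test then agrees with the numerator either way.

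The cost is a few reworded sentences. Call time is already to be recorded and the numerator is already defined, so no new data are needed unless mailing costs are netted; in that case they must be recorded too, because delivery costs are planned for the intervention group only. The downside is that a programme inside the band loses the cost-saving label.
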